#### 6.5. Patient Withdrawal

Patients may withdraw from the treatment/trial at any time at their own request, or they may be withdrawn at any time at the discretion of the investigator or sponsor for safety, behavioral, or administrative reasons. If a patient does not return for a scheduled visit, every effort should be made to contact the patient. In any circumstance, every effort should be made to document patient outcome, if possible. The investigator should inquire about the reason for withdrawal, request that the patient return all unused investigational product(s), request that the patient returns for a final visit, if applicable, and follow-up with the patient regarding any unresolved adverse events.

#### 6.5.1. Withdrawal from treatment

Patients will be withdrawn from treatment in the case of:

- Recurrence or occurrence of a secondary malignancy. Investigators are encouraged
  to await the result of the IRC assessment before making treatment decisions unless
  clinical considerations require immediate intervention eg, in the case of brain
  metastases;
- Unacceptable toxicity;
- Need for anticancer therapy not specified in the protocol;
- Congestive heart failure;
- Repeated noncompliance;
- Patient becomes pregnant;
- Patient lost to follow-up;
- Patient choice to withdraw from treatment (follow-up permitted by patient)

If patients require >2 consecutive weeks of dose interruption, a discussion should be made in consultation with the medical monitor.

Data to be collected for the end of study treatment/withdrawal from treatment are described in the End of Study Treatment/Withdrawal from treatment Procedures section (Section 6.2.3). Patients will be followed up for at least 28 days after the last dose of study drug for adverse events and concomitant medications and treatments

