## 5.3.4.1. Management of Axitinib/Placebo-Related Adverse Events

This section contains management of adverse events except hypertension and proteinuria which are discussed in subsequent sections.

The criterion for dose modification for study-drug-related adverse events is summarized in the table below:

Table 3 Criteria for Dose Modification for Axitinib/Placebo – Related Adverse Events Other Than Hypertension Or Proteinuria

Related Adverse Events	Intervention
Grade 1	Continue at same dose level.
Grade 2*	Continue at same dose level or decreased dose to one
	lower dose level. a)
Grade 3*	Interrupt dosing; re start at one or two lower dose level
	as soon as improvement to CTCAE Grade ≤1 or
	baseline. b) Discontinue dosing in case of grade 3
	persisting for $\geq 2$ weeks or grade 3 despite dose
	reduction to 1 mg BID.
Grade 4 or RPLS**	Discontinue dosing

\* Patients who have a grade 3 arterial event, grade 3 hemorrhagic event, grade 3 perforation/fistula, grade 3 palmar-planter erythrodysesthesia syndrome (PPE), or persistent grade 2 PPE despite dose reduction to 1 mg BID, should be discontinued dosing.

- a) Dose may be decreased to one lower dose level if the investigator considers it is difficult to continue treatment at same dose level.
- b) Dose may be decreased to two lower dose level if the investigator considers it is difficult to continue treatment at one lower dose level.

\*\* Treatment interruption for patients with signs/symptoms of reversible posterior leukoencephalopathy (RPLS). RPLS is a neurological disorder which can present with headache, seizure, lethargy, confusion, blindness and other visual and neurologic disturbances. Mild to severe hypertension may be present. Magnetic resonance imaging is necessary to confirm the diagnosis of RPLS. In case of confirmed diagnosis discontinue permanently.

Dose may also be interrupted or decreased at the discretion of the investigator even if none of the above criteria applies.

Guidelines for dose reductions for specific adverse events are provided in the following sections.

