##### 4.4. Protocol Deviations

---

|           |   |                 |           |
|-----------|---|-----------------|-----------|
| Document: | C:\Users\q764206\AppData\Local\Microsoft\Windows\Temporary Internet Files\Content.Outlook\GWW33WM3\ATLAS_SAPFinal v8.0_06MAR2018.docx |                 |           |
| Author:   | [name] (Updated [name]; [name]; [name], [name])  | Version Number: | Final 8.0 |
|           |   | Version Date:   | 06MAR2018 |

Template No: CS\_TP\_BS016 – Revision 2  
Effective Date: 01Feb2010

Reference: CS\_WI\_BS005

Statistical Analysis Plan

---

Subjects with major protocol deviations will be summarized by treatment group.

Major protocol deviations include, but are not limited to:

- Subjects who did not meet inclusion/exclusion criteria or eligibility was not adequately verified
- Received prohibited concomitant medications post-baseline
- Developed withdrawal criteria but were not withdrawn
- Has a dosing error likely to impact key outcome measures (for example subject did not receive the medication they were randomized to receive)

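### Protocol 6.5.1 withdraws patients for congestive heart failure without qualification, while Table 3 continues or restarts dosing for drug-related events at Grade 1, Grade 2 and recovering Grade 3

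*Protocol*

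**What the plan says.** Protocol 6.5.1 opens its list with mandatory wording: "Patients will be withdrawn from treatment in the case of". One item is "Congestive heart failure". It carries no grade, relatedness, symptom or reversibility condition and does not point to Table 3.

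Protocol 5.3.4.1 defines its reach broadly: "This section contains management of adverse events except hypertension and proteinuria which are discussed in subsequent sections". It then limits the table to events related to study drug: "The criterion for dose modification for study-drug-related adverse events is summarized in the table below". The Table 3 rows read:

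- Grade 1: "Continue at same dose level".
- Grade 2: "Continue at same dose level or decreased dose to one" lower level.
- Grade 3: "Interrupt dosing; re start at one or two lower dose level", on improvement to Grade 1 or less or baseline. Dosing is discontinued if Grade 3 lasts 2 weeks or more, or occurs despite reduction to 1 mg BID.
- Grade 4, or RPLS: discontinue.

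A footnote to Table 3 adds events that end dosing: Grade 3 arterial, hemorrhagic, perforation/fistula and PPE events, and persistent Grade 2 PPE at 1 mg BID. Heart failure is not named.

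SAP 4.4 counts among major protocol deviations those who "Developed withdrawal criteria but were not withdrawn".

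**The concern.** A site with a patient who has drug-related heart failure can find two instructions. The withdrawal list ends treatment. The dose-modification table may keep the patient on drug or bring the patient back to it. Protocol 5.3.3 sends patients with a drug reaction to Section 5.3.4, so a site may well reach Table 3 first, and nothing there points on to 6.5.1.

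Three things are at stake. The first is safety: whether a patient with a cardiac event continues study drug should not depend on which page the site opened. The second is deviation classification: following Table 3 to the letter produces a major deviation under SAP 4.4. The third is reporting. SAP 7.5.1.2 makes congestive heart failure/cardiomyopathy an event category of special interest. SAP 7.5.1 separates events leading to dose reduction, temporary interruption and permanent discontinuation, and SAP 7.3.4 plans the cumulative incidence of discontinuation for defined events of interest. For heart failure, those outputs would partly reflect which section each site used.

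**Working it through.** No arithmetic applies. The check sets the two protocol sections side by side for each type of heart failure event.

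| Heart failure event | Protocol 6.5.1 | Protocol 5.3.4.1, Table 3 | Result |
|---|---|---|---|
| Unrelated to study drug | Withdraw | Table does not apply | No conflict |
| Related, Grade 1 | Withdraw | Continue | Conflict |
| Related, Grade 2 | Withdraw | Continue, or one level lower | Conflict |
| Related, Grade 3, recovering to Grade 1 or less or baseline before the 2-week limit | Withdraw | Interrupt, then restart one or two levels lower | Conflict |
| Related, Grade 3, lasting 2 weeks or more | Withdraw | Discontinue | Agree |
| Related, Grade 3, despite reduction to 1 mg BID | Withdraw | Discontinue | Agree |
| Related, Grade 4 | Withdraw | Discontinue | Agree |

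The conflict is therefore confined to three of the seven situations, all of them drug-related.

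Next, does any other text settle which section governs?

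- *Scope of 5.3.4.1.* It carves out hypertension and proteinuria and nothing else. Heart failure is inside its stated scope.
- *Exceptions within Table 3.* RPLS and the footnote show that the table names event-specific stops where it wants them. Heart failure is not one of them.
- *Investigator discretion in 5.3.4.1.* The closing sentence allows interruption or reduction outside the table. It does not mention withdrawal.
- *Qualifiers elsewhere.* Exclusion criterion 4 restricts heart failure to symptomatic disease; 6.5.1 has no such word. The intended scope of the 6.5.1 item cannot be inferred from how the term is used elsewhere in the protocol.
- *Cross-references.* Sections 5.3.4.1 and 6.5.1 do not refer to each other on this point, and neither states precedence.

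Last, does the conflict reach the primary analysis? Efficacy is analysed in the intent-to-treat population (Protocol 9, SAP 4.1). No per-protocol population is defined. SAP 4.4 only summarises major deviations by treatment group. Protocol 6.4 continues DFS and OS follow-up however long treatment lasted. The DFS censoring rules in SAP 5.1 and Appendix A turn on scans and further anti-tumor therapy, not on stopping study drug. The analysis set, follow-up and event rules for DFS are therefore untouched.

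**The case against.** The strongest reply is that the texts can be read together. Section 6.5.1 is a specific, mandatory list that names heart failure; Table 3 is a general grade table that does not. On the usual principle that the specific rule controls, 6.5.1 decides who leaves treatment and Table 3 manages those who stay. Section 6.5 also lets the investigator withdraw a patient for safety at any time, so withdrawing breaches neither section, whereas re-dosing breaches 6.5.1. The Table 3 footnote does not claim to be exhaustive. SAP 4.4 treats the withdrawal criteria as binding.

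This is a plausible reading, and it may be what was intended. It does not remove the point, because no sentence states it. Section 5.3.3 sends drug reactions to Section 5.3.4, whose declared scope includes heart failure. SAP 4.4 classifies deviations after the fact; it is not an instruction that a site would consult when deciding on treatment.

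Several limits do stand:

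- A reader might infer that every related Grade 1 to 3 event meets opposite instructions and that only Grade 4 agrees. The Grade 3 row does not support this: it ends dosing for persistent events and for events at the lowest dose level, and it makes restart conditional on recovery.
- That 6.5.1 applies at every grade is the plain reading of an unqualified list item, not its wording. CTCAE definitions are cited in Protocol Appendix 3 but not reproduced, so the documents alone do not show whether a Grade 1 or 2 event would be called congestive heart failure.
- A reader might size the problem by applying an assumed rate to the axitinib arm. At 1% to 3% of about 350 patients (700 / 2) that gives 3.5 to 10.5, or roughly 4 to 11. The documents give no such rate, and Table 1 of the protocol has no heart failure row. The count would also include unrelated, Grade 4 and persistent Grade 3 events, where there is no conflict.

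**Conclusion.** The conflict is real and narrow. For drug-related heart failure at Grade 1, Grade 2 and recovering Grade 3, one section withdraws the patient and the other continues, reduces or restarts study drug, with no stated precedence. It rests on two assumptions: that the unqualified item in 6.5.1 means what it says, and that a drug-related heart failure event falls under 5.3.4.1 because it is not carved out.

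Its weight comes from patient safety, from a deviation rule that penalises a site for following the dose-modification table, and from discontinuation and dose-modification summaries that could mix two practices. How many patients it touches cannot be derived from the documents. A reader might infer a threat to the primary DFS result; the intent-to-treat analysis, continued follow-up and censoring rules do not support that.

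**What to change.** Reconcile Protocol 5.3.4.1 (Table 3 and its footnotes) with Protocol 6.5.1 so that both state the same scope for heart failure, covering grade, relatedness and any condition for resuming, and have each refer to the other. Which rule applies is for the sponsor's clinicians to decide; no view is taken here. Then align the SAP 4.4 deviation check with the reconciled text, and say how patients handled before the clarification will be classified.

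The cost is a few lines in the protocol, a notice to sites and one adjusted deviation check. No procedures, visits or patients are added.

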#### 6.5.2. Withdrawal from trial

If the patient withdraws from the trial and also withdraws consent for disclosure of future information, no further evaluations should be performed and no additional data should be collected. Sponsor may retain and continue to use any data collected before such withdrawal of consent.

#### 7. ASSESSMENTS

#### 7.1. Efficacy Assessments

Local and the IRC imaging tumor assessments are to be performed between week 3-8 post-nephrectomy. Brain CT or MRI within 12 weeks prior to randomization is acceptable regardless of whether it is before or after nephrectomy.

During the trial, local and the IRC imaging tumor assessments will be performed (regardless of the duration of treatment) every 16 weeks during the first 3 years of study (also, at the end of treatment) and every 6 months thereafter until the time for final analysis, or recurrence or occurrence of a secondary malignancy, whichever comes first.

Investigators are encouraged to await the result of the IRC assessment before making treatment decisions for patients who require palliative radiotherapy because of suspected recurrence or occurrence of a secondary malignancy unless clinical considerations require immediate intervention eg, in the case of brain metastases. In the event that an investigator determines recurrence or occurrence of a secondary malignancy based on local imaging reviews and/or local histo-/cytopathology reports, the patient must continue to receive tumor assessments until the IRC determines recurrence or occurrence of a secondary malignancy.

Local and IRC imaging assessments at screening and during the trial will include CT or MRI of the brain, chest, abdomen and pelvis, and other applicable sites. Further imaging techniques e.g., bone scan, are to be performed as clinically indicated if metastases are present or suspected.

For patients who present with findings suggestive of a tumor recurrence or secondary malignancy, histo-/cytopathological confirmation of the diagnosis should be obtained except in patients whose suspicious lesions are deemed by the investigator not to be amenable to biopsy. Such available local histo-/cytopathology reports should be submitted to the IRC for review in cases for which there is site confirmation of recurrence or occurrence of a secondary malignancy in the absence of IRC imaging confirmation. For patients with an isolated, suspected intracranial recurrence, histologic documentation of recurrence in surgically accessible lesions is highly recommended, but not required. For such patients, document the recurrent disease using MRI or CT if MRI is not generally available or is contraindicated.

The diagnosis of a recurrence or occurrence of a secondary malignancy can be made only when the imaging, clinical or pathology findings meet at least one of the following acceptance criteria:

#### Lung

- a. Positive cytology or histology.
- b. Imaging evidence of lesions felt to be consistent with metastases.
- c. Proof of neoplastic pleural effusion should be established by cytology or pleural biopsy.

#### Liver

- a. Positive cytology or histology.
- b. New focal defects on MRI or CT that are enlarging in size as documented by at least a 4-week interval.
- c. Proof of neoplastic abdominal ascites established by cytology or histology.

#### **Central Nervous System**

- a. Positive brain CT or MRI.
- b. Positive cerebral spinal fluid (CSF) cytology.

#### **Subcutaneous and Lymph Node Recurrence**

- a. Positive histology.
- b. Progressively enlarging solid mass or node(s) as evidenced by two CT or MRI separated by at least a 4-week interval.
  - · Nodal lesions must have a short axis diameter ≥10 mm to be considered enlarged.

#### Skeletal

- a. Positive radiographic study such as bone scan (confirmatory imaging in addition to bone scan may be required).
- b. For a solitary lesion or equivocal finding on imaging, a positive histology.

#### **Other Organs**

- a. Histology/aspiration cytology.
- b. Progressively enlarging solid mass or node(s) as evidenced by two CT or MRI separated by at least a 4-week interval.
  - · Nodal lesions must have a short axis diameter  $\geq 10$  mm to be considered enlarged.
- c. Urethral obstruction in the presence of a mass as documented on CT or MRI.

Anything not meeting the above criteria should be considered unacceptable for evidence of recurrence or occurrence of a secondary malignancy and should not be an indication to alter protocol therapy.

## 7.1.1. Primary Endpoint

DFS is defined as the time interval from the date of randomization to the first date of recurrence (distant or local recurrence of RCC) or the occurrence of a secondary malignancy or death. The primary DFS analysis will be based on assessments by the IRC. IRC will review all imaging data. Additionally, in cases for which there is site confirmation of recurrence or occurrence of a secondary malignancy in the absence of IRC imaging

confirmation, available local histo-/cytopathology reports will also be reviewed by the IRC oncologist to determine confirmation of recurrence or occurrence of a secondary malignancy.

Recurrence refers to relapse of the primary tumor in situ or at metastatic sites. The date of recurrence or the occurrence of a secondary malignancy is defined as the date of the tumor scan or the date of collection of the histo-/cytopathological specimen (for patients who have site confirmation of recurrence or occurrence of secondary malignancy in the absence of IRC imaging confirmation) that demonstrated unequivocal recurrence or a secondary malignancy according to protocol criteria. If both imaging and histo-/cytopatholigical confirmation of recurrence or sencondary malignancy are available, the earlier of the two dates will be considered.

For patients with no DFS event, DFS time will be censored at the date of the last scan prior to the time for the analyses. Patients alive who do not have post-baseline disease assessments will have their DFS times censored at randomization. For patients receiving further anti-tumor therapy prior to recurrence or occurrence of a secondary malignancy or death, DFS will be censored on the date of the last scan prior to taking the anti-tumor medication. Patients who miss 2 or more consecutive tumor scans immediately followed by an event will be censored at the date of the last objective tumor assessment prior to the missing/not readable scans.

## 7.1.2. Secondary Endpoints

OS is defined as the time from the date of randomization to the date of death due to any cause. In the absence of confirmation of death, survival time will be censored at the last date the patient is known to be alive. Patients lacking data beyond randomization will have their survival times censored at randomization.

## 7.2. Safety Assessments

#### 7.2.1. Adverse Events

Assessment of adverse events will include: type, incidence, severity (graded by the National Cancer Institute [NCI] Common Terminology Criteria for Adverse Events [CTCAE], Version 4.0), timing, seriousness, and relatedness; and laboratory abnormalities.

Baseline tumor-related signs and symptoms will be recorded as adverse events during the trial if they worsen in severity or increase in frequency.

#### 7.2.2. Laboratory Safety Assessments

Hematology and blood chemistry will be drawn at the time points described in the Schedule of Activities and analyzed at central laboratories (Refer to Appendix 1). Investigators may have additional blood tests performed for the purpose of planning treatment administration, dose modification, or following adverse events and should be repeated as clinically needed. PT/INR should be performed to monitor patients receiving concomitant warfarin or other anti-coagulants and when clinically indicated.

Thyroid Function Tests (TSH, free T3 and free T4) should be performed for all patients at baseline (Cycle 1Day 1 pre-dose). Subsequently TSH should be done at Cycle 1 Day 15, Cycle 2 Day 1, Cycle 3 Day 1, Cycle 4 Day 1, Cycle 5 Day 1, then every 8 weeks thereafter starting from Cycle 7 Day 1. TSH, free T3, free T4 should be performed on the next visit for any patient who has an elevated TSH in the previous visit. Hypothyroidism should be treated per standard medical practice to maintain euthyroid state with a normal TSH.

## 7.2.3. Other Safety Assessments

**Physical examination**: A physical examination including, but not limited to, general appearance, head, skin, neck, eyes, ears, nose, mouth, throat, breast, lungs, heart, abdomen, back, lymph nodes, extremities, thyroid, musculoskeletal, pulses and nervous system will be performed. The physical examination will include examination of known and suspected sites of disease.

**Height and body weight**: Height will be recorded at screening visit only. Body weight will also be recorded at the start of each 4 week period.

**Vital Signs**: Measurements will be made of temperature, BP and pulse rate. 2 BP readings should be taken at least 5 minutes apart in the seated position after the patient has been sitting quietly for 5 minutes.

All patients will be issued a blood pressure monitor and blood pressure measurement diary. Patients will be asked to record their blood pressure measurements prior to taking each dose of study drug (twice daily) for the first 3 months, and once a week thereafter. Following dose modification of study drug or anti-hypertensive medication, or changes of anti-hypertensive medication, patients should restart blood pressure measurements prior to taking each dose of study drug for the first 3 months and once a week thereafter. Patients should record all blood pressure measurements in their patient diary. BP readings should be taken in the seated position after the patient has been sitting quietly for 5 minutes. Patients should be instructed to inform the investigator immediately if their sBP rises above 150 mm Hg, dBP rises above 100 mm Hg, or if they develop symptoms perceived to be related to elevated BP (eg, headache, visual disturbance).

**ECOG PS**: The ECOG PS scale will be used (Appendix 2). Evaluation of ECOG PS at screening should reflect the patient condition just prior to nephrectomy.

All safety assessments should be repeated as clinically needed.

#### 8. Adverse Event Reporting

## 8.1. Adverse Events

All observed or volunteered adverse events regardless of treatment group or suspected causal relationship to the investigational product(s) will be reported as described in the following sections.

For all adverse events, the investigator must pursue and obtain information adequate both to determine the outcome of the adverse event and to assess whether it meets the criteria for classification as a serious adverse event (See Section 8.5) requiring immediate notification to sponsor or its designated representative. For all adverse events, sufficient information should be obtained by the investigator to determine the causality of the adverse event. The investigator is required to assess causality. For adverse events with a causal relationship to the investigational product, follow-up by the investigator is required until the event or its sequelae resolve or stabilize at a level acceptable to the investigator, and sponsor concurs with that assessment.

